4.1.1 Inclusion Criteria

Patients must meet the following criteria for study entry:

1. Male and female patients aged 40–80 years, inclusive.
2. Clinical symptoms consistent with IPF of ≥ 6 months duration.
3. Patients should have both “confident” or “consistent” with UIP diagnosis of IPF based on clinical, radiologic or pathologic data according to 2011 ATS/ERS guidelines at the Screening. HRCT scan performed within 24 months before the start of the Screening may be used.
4. No features supporting an alternative diagnosis on transbronchial biopsy, bronchoalveolar lavage (BAL), or surgical lung biopsy, if performed. Results of the surgical lung biopsy performed within the last 4 years must be confirmed by central review.
5. Patients with %FVC ≥ 40 % at the Screening.
6. Patients with %DL_{CO} ≥ 30 % at the Screening.
7. Ability to walk ≥ 100 m during the 6-minute walk test at the Screening.
8. Eligible patients must discontinue all prohibited medications at least 28 days before the *start of treatment*.
9. Female patients of childbearing potential must have negative urine pregnancy test at the Screening and before first dosing on Day 1.

Pirfenidone—F. Hoffmann-La Roche Ltd

10. Patients able to conceive must agree to use safe contraceptive methods for the whole duration of the study and 28 days after the last dosing.

- a. For women of childbearing potential: agreement to remain abstinent (refrain from heterosexual intercourse) or use a highly effective contraceptive method with a failure rate of < 1% per year during the treatment period and for at least 28 days after the last dose of pirfenidone. A woman is considered to be of childbearing potential if she is postmenarcheal, has not reached a postmenopausal state (≥ 12 continuous months of amenorrhea with no identified cause other than menopause), and has not undergone surgical sterilization (removal of ovaries and/or uterus). Examples of highly effective contraceptive methods with a failure rate of < 1% per year include bilateral tubal ligation, male sterilization, hormonal contraceptives that inhibit ovulation, hormone-releasing intrauterine devices (IUD), and copper intrauterine devices.
- b. For men: agreement to remain abstinent (refrain from heterosexual intercourse) or use contraceptive measures, and agreement to refrain from donating sperm, as defined below:

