**ML39355_STATISTICAL ANALYSIS PLAN_Final 2.0_17 June 2020**

permanent use of corticosteroids (prednisolone at a maximum daily dose of 15 mg or equivalents) and brief periods of corticosteroid use for acute IPF exacerbation, patients will not receive any other therapy for the treatment of IPF. After central review of HRCT and SLB, patients will enter the Screening period, which may last up to 28 days (4 weeks).

After the Screening, eligible patients will enter the Treatment period lasting 26 (\pm 1) weeks. All patients will receive pirfenidone 2403 mg/d administered orally in divided doses three times per day (TID) with food. Dose of the study treatment will be titrated over 14 days to the full dose of 9 capsules per day (three 267 mg capsules taken orally TID with food). Patients will remain on a stable maintenance dose for the duration of the treatment period unless the dose is reduced to manage adverse events or titrated again when restarting study treatment after an appropriate interruption in treatment.

The primary efficacy endpoint in the study is the change from baseline to Week 26 in absolute (mL) FVC and relative (%) FVC as measured by spirometry procedure. Spirometry will be performed at the Screening, on Day 1 of treatment, at Week 12, Week 26 and in the extended Follow-up period (Weeks 39 and 52), if applicable. At screening, spirometry measurements will be performed before and after administration of albuterol (or salbutamol) from a metered dose inhaler. During further visits, bronchodilator test is not necessary to perform. Spirometry data collected throughout the study will be evaluated by local readers.

Patients will have a telephone assessment at Week 1, when safety-related information and adherence to treatment is collected. Subsequently patients will have in-clinic visits at Weeks 2, 4, 8, 12, 16, 20 and 26. Patients should complete an adverse event and dosing compliance diary between all visits. Additionally, telephone calls to patients will be scheduled at Weeks 3, 5, 7, 13 and 24 as a part of IPF care program. A total of 5-7 calls are scheduled in the study, including extra-calls at Weeks 8 and 10 as needed.

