6.3. Missing Data⁴

For missing FVC data imputation, patients will be classified into different patterns depending on the availability of data:

Patients with a 26 week FVC value:

1. those who received study drug until 26 weeks (completed the treatment period);
2. those who prematurely discontinued study drug, but who were followed up until Week 26.

Patients without a 26 Week FVC value:

3. those who were alive at 26 weeks;
4. those who died before 26 weeks.

Missing data at other visits before Week 26 (primary outcome variable) will not be imputed.

The following imputation methods including sensitivity analyses will be applied for patients with pattern 3 - 4:

Assuming that deaths of the patients (pattern 4) is likely to be related to worsening of IPF, these unobserved FVC values should be lower than those in patients who did not die prior to Week 26.

Methods for handling missing data due to death will include the following:

- Replacement with the worst possible value (FVC= 0 mL or 0%) (Primary analysis).
- Replacement with worst observed averaged FVC value at week 26 (Sensitivity analysis).

⁴ This section is based on the section 6.2 “Summaries of conduct of study” of clinical study Protocol.

ML39355_STATISTICAL ANALYSIS PLAN_Final 2.0_17 June 2020

- Replacement with an intermediate value (FVC =1500 mL or 50%) (Sensitivity analysis).

Missing data due to reasons other than death (e.g., missing visits, early withdrawal from the study, including missing values due to lung transplantations) (pattern 3) will be replaced with imputed values based on the average measurements for “similar” patients at that time point. Similar patients are those without missing data before that time point and whose data have the smallest sum of squared deviations (SSD) from that patient for all visits prior to the one with the missing data. Missing data due to lung transplant will be imputed using the SSD method even if the patient dies after lung transplant.

The procedure referred to as the sum of squared deviations (SSD) is outlined as follows:

Step 1: For post-Baseline missing value to be imputed at a visit (Visit week 26) for a particular patient (Patient A), a set of all patients without any missing values for visits from Baseline up to Visit week 26 as Patient A will be selected.

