Step 2: For the patients in this set, the SSDs between each patient selected in Step 1 and Patient A will be calculated across all non-missing values from Baseline up to the visit prior to Visit week 26.

Step 3: The 3 patients with the smallest SSDs will be identified and the average of their non-missing value at Visit week 26 will be used to impute the missing value for Patient A at that visit. The number of smallest SSDs to calculate the average can be less than 3 due to availability of patients defined in Step 1 or more than 3 based on tied SSDs.

A sensitivity analysis will use the data imputed with last observation carried forward method (LOCF).

Complete case analysis will also be performed as a sensitivity analysis.

If the information about end date for prior/concomitant therapy is missing or incomplete, the following rules (table 6.1) will be used for the classification of therapy as prior or concomitant.

Table 6.1 – Management of partial and missing prior/concomitant therapy end date.

Day	Month	Year	Processing
is missing	is known	is known	Therapy will be classified as concomitant, if month and year \geq month and year of the first dose of study therapy, else – as prior
is missing	is missing	is known	Therapy will be classified as concomitant, if year \geq year of the first dose of study therapy, else – as prior
is known	is missing	is known	
is missing	is known	is missing	Therapy will be classified as concomitant
is known	is missing	is missing	
is missing	is missing	is missing	

ML39355_STATISTICAL ANALYSIS PLAN_Final 2.0_17 June 2020

If the information about adverse event start date and time is missing or incomplete, the following rules (table 6.2) will be used for the classification of adverse events as TEAEs and non-TEAEs (occurred before the start of study treatment).

Table 6.2 – Management of partial and missing AE start date.

Day	Month	Year	Processing
is missing	is known	is known	AE will be classified as TEAE, if month and year \geq month and year of the first dose of study therapy
is missing	is missing	is known	AE will be classified as TEAE, if year \geq year of the first dose of study therapy
is known	is missing	is known	
is missing	is known	is missing	AE will be classified as TEAE
is known	is missing	is missing	
is missing	is missing	is missing	

No date imputation will be performed for listings.

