8.1. Primary Efficacy Analysis

The primary outcome variable is the absolute change in FVC from Baseline to Week 26 (both in mL and % predicted). Baseline FVC will be the average of the FVC measured at the Screening (excluding values after bronchodilator administration) and Day 1 visits, if either is missing, the non-missing value will be used. The FVC at Week 26 will be the average of the FVC measured on

¹⁰ This section is based on the section 6.4 “Efficacy analyses” of clinical study Protocol.

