**ML39355_STATISTICAL ANALYSIS PLAN_Final 2.0_17 June 2020**

two separate days at Week 26, if either is missing, the non-missing value will be used. If both values are missing, the data will be imputed as specified in Section 6.3.

Data will be analyzed using standard descriptive statistics for continuous variables and 95% CI for the means and mean changes.

The data imputation methods for primary endpoint are described in Section 6.3.

For the primary analysis, missing data due to death will be replaced with the worst possible value (FVC= 0 mL or 0%). Missing data due to reasons other than death (pattern 3) will be replaced with imputed values based on the average measurements for “similar” patients at that time point (SSD, Primary analysis).

As sensitivity analyses, the following imputation methods will be used:

1. Missing data due to death will be replaced with the worst observed FVC value at week 26. Missing data due to reasons other than death (pattern 3) will be replaced with imputed values based on the average measurements for “similar” patients at that time point (SSD).

2. Missing data due to death will be replaced with an intermediate value (FVC =1500 mL or 50%). Missing data due to reasons other than death (pattern 3) will be replaced with imputed values based on the average measurements for “similar” patients at that time point (SSD).

3. Missing data due to death will be replaced with the worst possible value (FVC= 0 mL or 0%). Missing data due to reasons other than death (pattern 3) will be replaced with LOCF.

4. Missing data due to death will be replaced with the worst observed FVC value at week 26. Missing data due to reasons other than death (pattern 3) will be replaced with LOCF.

5. Missing data due to death will be replaced with an intermediate value (FVC =1500 mL or 50%). Missing data due to reasons other than death (pattern 3) will be replaced with LOCF.

6. Missing data due to death and due to reasons other than death (pattern 3) will be replaced with LOCF.

Analysis of the primary efficacy endpoint will be also repeated on the Complete case set (CCS) without missing data imputation as the sensitivity analysis. Complete case set will include patients related to pattern 1 and 2 (section 6.3), results will be reported for pattern 1 and 2 separately and overall.

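### The primary SSD imputation carries over the donors' Week 26 FVC level, not their change, which biases drop-outs at the low extreme of FVC towards no decline or improvement

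*SAP*

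**What the plan says.** The primary outcome in SAP 8.1 is the absolute change in FVC from Baseline to Week 26, in mL and in % predicted. For a patient who is alive but has no Week 26 FVC, SAP 8.1 makes the sum-of-squared-deviations (SSD) method the primary handling.

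SAP 6.3 defines similar patients as those "whose data have the smallest sum of squared deviations (SSD) from that patient for all visits prior to the one with the missing data". Step 2 computes the SSD "across all non-missing values from Baseline up to the visit prior to Visit week 26". Step 3 takes as donors the three candidates whose SSDs are lowest, then states that "the average of their non-missing value at Visit week 26 will be used to impute the missing value for Patient A at that visit". Fewer or more than three donors are possible if candidates are few or tied. No step adjusts for a baseline difference between donors and patient, and no limit is set on how far away a donor may be.

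Little FVC data is available for matching. SAP 4.1 states: "Spirometry will be performed at the Screening, on Day 1 of treatment, at Week 12, Week 26". Before Week 26 that leaves Baseline (the average of Screening and Day 1) and Week 12. Entry requires "Patients with %FVC ≥ 40 % at the Screening" (Protocol 4.1.1). Protocol 6.2 describes the same method in less detail, also as an average of similar patients' measurements at the missing time point. SAP Section 14 declares the SAP fully consistent with the Protocol.

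**The concern.** The rule imputes a level, while the analysis uses a change. Any difference in FVC between the donors and the patient before drop-out passes straight into the imputed change. In the middle of the FVC range donors lie on both sides and the differences tend to cancel. At the bottom there are few or no patients below, so the nearest donors lie mostly above and the difference is booked as FVC gain. At the top it is booked as loss.

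The study has no comparator. If low-FVC patients are the ones who drop out, an upward error flatters the drug and no control arm offsets it. The result enters the primary row of SAP Table 2.2 and, for the patients concerned, their category in Table 2.3.

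**Working it through.** **1. The plan's own figures.** SAP Section 5: n = 0.601 × 0.399 × (1.96/0.125)² = 58.96, as stated. The half-width for mean change is 1.96 × 20/√60 = 5.06, stated as about 5. The SAP gives no figure for the SSD rule.

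**2. What the rule computes.** Let B_A be the patient's baseline, B_D the donors' mean baseline and W_D their mean Week 26 value.

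Imputed change = W_D − B_A = (B_D − B_A) + (W_D − B_D) = baseline gap + donors' mean change.

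The first term is a matching error, not a change over time.

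**3. Size at the low extreme.** Inputs from SAP Section 5: 60 patients; % predicted FVC 67.8 (SD 11.24) at baseline and 65.3 (SD 14.52) at Week 26; mean change 65.3 − 67.8 = −2.5. The floor of 40 is from Protocol 4.1.1. Assumed, because the documents are silent: baseline-to-Week 26 correlation r, visit measurement SD of 2 points, linear decline, 44 to 59 available donors.

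The two stated SDs fix the slope of change on baseline at r × 14.52/11.24 − 1. This is 0 at r = 0.774 and 0.163 at r = 0.90. The lowest of 60 has a baseline of about 44.3, so the expected change is −2.5 at r = 0.774, and −2.5 + 0.163 × (44.3 − 67.8) = −6.3 at r = 0.90. Simulated averages for that patient (sums agree up to rounding):

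| r | Matched on | Gap | Donors' mean change | Imputed change | Expected | Error |
|---|---|---|---|---|---|---|
| 0.774 | Baseline | 4.82 | −2.26 | +2.57 | −2.5 | +5.1 |
| 0.774 | Baseline, Week 12 | 5.49 | −5.07 | +0.42 | −2.5 | +2.9 |
| 0.90 | Baseline | 4.82 | −5.23 | −0.41 | −6.3 | +5.9 |
| 0.90 | Baseline, Week 12 | 5.24 | −6.89 | −1.64 | −6.3 | +4.7 |

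The gap is about 5 points throughout. When Week 12 is in the match, part of it is offset, because the selected donors are those who had fallen more. The effect fades quickly with rank. Over r from 0.70 to 0.90 the gap is 1.7 to 2.8 points for the second-lowest patient and 0.6 to 1.5 for the third-lowest. For the highest patient the donors lie about 7 points lower, and the imputed change is about −8 to −10 (change SD 6.6, unrelated to baseline).

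**4. Effect on the trial mean.** Trials of 60 were simulated with matching on Baseline and Week 12. Assumed selection: drop-out odds multiplied by e for every 10 points lower FVC at Week 12. With both stated SDs, r = 0.85 to 0.90 and 6 missing:

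| Method | Mean change |
|---|---|
| Truth | −2.5 |
| SSD level, as planned | −2.3 |
| LOCF | −2.2 to −2.3 |
| Complete case | −2.1 to −2.2 |
| Last observed value plus donors' change | −2.5 |

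Over all scenarios with FVC-related drop-out, the planned rule understates the decline by about 0.1 to 0.2 points with 6 missing and 0.3 to 0.5 with 12, and by up to about 0.8 under steeper selection. With missingness unrelated to FVC there is no overall bias. Across 24 scenarios, imputing donor change stayed within about 0.1 point of the true mean and had a smaller root mean squared error than imputing level, including under random missingness.

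**The case against.** A reader might infer that a low-FVC drop-out is typically entered as having improved, and that Table 2.3 is inflated as a result. The documents do not support this. Under the SAP's baseline distribution, the probability of a baseline of 40 to 45% is 0.0147, or 0.88 patients of 60, and (1 − 0.0147)^60 = 41% of trials have none. With 6 missing under moderate selection, drop-outs in that band number about 0.4 to 0.5 per trial. When the stated Week 26 SD of 14.52 is respected, about 54% of them are imputed as improved (46 to 62% across runs). Shares of 73 to 93% arise only if that SD is ignored and change SDs of 3 to 7 points are assumed. Over all drop-outs with 6 missing, 17 to 28% were imputed as improved, within 2 points of the truth in every scenario run.

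The effect on the mean is also small. A single death set to 0% moves it by about 65.3/60 = 1.1 points, and even with a change SD of 7 the half-width would be 1.96 × 7/√60 = 1.8. No hypothesis test is attached to the primary endpoint.

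The driver is assumed. Nothing in the documents says that drop-outs come from the low end. Protocol 4.1.2 excludes patients with life expectancy under 12 months or on an active transplant list, and those who stop the drug are asked to stay through Week 26. Pointing the other way, SAP 6.3 treats lung transplantation as a source of these missing values and links deaths to worsening disease.

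Finally, LOCF and complete-case analyses are planned and use no donor levels. That is true, but in the runs above both erred in the same direction as the planned rule, so agreement among them would not show that the primary result is sound.

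What stands of the objection: the consequence is modest and conditional. It does not touch the mechanism, which follows from Step 3 as written.

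**Conclusion.** The concern holds in a limited form. The primary SSD rule transfers a level into a change endpoint, with no anchoring and no distance limit. For the lowest of 60 patients the gap of about 5 points is booked as gain. The net error is about 3 to 6 points under the assumptions shown, which moves that patient towards no decline or improvement without making improvement the usual result. The reverse holds at the top.

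The mean decline is understated only if drop-out rises as FVC falls: by about 0.1 to 0.2 points of 2.5 with 6 missing and 0.3 to 0.5 with 12, more under steeper selection. Against a planned half-width of about 5 this will not overturn the result. It is worth correcting because the remedy needs no data, performed at least as well in every scenario tried, and the planned sensitivity analyses may not reveal the error. The correlation, the drop-out rate and the drop-out pattern are not in the documents.

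**What to change.** In SAP 6.3 Step 3, keep the same donors and the same SSDs. Impute the patient's last observed FVC (Week 12, otherwise Baseline) plus the donors' mean change from that same visit to Week 26. Apply the rule to both mL and % predicted.

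The anchor should be the last observed visit. With Week 12 in the match and r = 0.774, the donors' change from Baseline is −5.07 where −2.5 is expected, so adding it to the patient's Baseline would overshoot by about 2.6 points.

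The cost is one sentence in the SAP and a small program change, with no new data. The downside is a departure from Protocol 6.2, which specifies the average of similar patients' measurements. Either align that wording or record the change in SAP Section 14, which now claims full consistency. Keep the level-based SSD as a sensitivity analysis so that the protocol-specified result is still reported.

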1. BACKGROUND

1.1 BACKGROUND ON IDIOPATHIC PULMONARY FIBROSIS

Idiopathic Pulmonary Fibrosis (IPF) is a chronic disease of unknown etiology that is characterized by progressive fibrotic destruction of the lung (predominantly of the lung interstitium), resulting in disabling dyspnea, poor gas exchange, decrease in lung volume, progressive pulmonary insufficiency typically leading to death. IPF is recognized by the American Thoracic Society (ATS) and European Respiratory Society (ERS) as a specific form of chronic, progressive fibrosing interstitial pneumonia of unknown cause, occurring primarily in older adults, limited to the lungs, and associated with the histopathologic and/or radiologic pattern of usual interstitial pneumonia (UIP) (ATS 2011).

IPF is a rare disease, it is estimated to affect about 1-5 in 10,000 persons in the European population (Orphanet). IPF is most prevalent in middle aged and elderly patients, and usually presents between the ages of 40 and 70 years (Esbriet EMA 2010); the mean age at presentation is 66 years (Orphanet). Although the disease is idiopathic by its nature, several potential risk factors have been identified. They include cigarette smoking, environmental exposures (metal, wood dust and other dusts), microbial agents (Epstein-Barr virus, cytomegalovirus, human herpesvirus), gastroesophageal reflux and genetic factors (ATS 2011).

Usual clinical findings of IPF include slowly increasing dyspnea and a nonproductive cough with progressive loss of lung volumes, i.e. decreased forced vital capacity (FVC), and decline in exercise tolerance. On high-resolution computed tomography (HRCT) scan, there are peripheral (subpleural), bibasilar, reticulonodular abnormalities with architectural distortion, honeycomb change, and traction bronchiectasis (ATS 2011; ATS 2015).

The diagnosis of IPF carries a bleak prognosis, the median survival for IPF patients is about 3 years from the time of diagnosis. However, the course of the disease varies from patient to patient. Slow progression of respiratory insufficiency is interspersed with episodes of acute exacerbation that accelerate decline and may be fatal (Collard et al. 2007).

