Missing data at other visits before Week 26 (primary outcome variable) will not be imputed.

The following imputation methods including sensitivity analyses will be applied for patients with pattern 3 - 4:

Assuming that deaths of the patients (pattern 4) is likely to be related to worsening of IPF, these unobserved FVC values should be lower than those in patients who did not die prior to Week 26. Methods for handling missing data due to death will include the following:

- Replacement with the worst possible value (FVC= 0 mL or 0%) (Primary analysis).
- Replacement with worst observed FVC value at week 26 (Sensitivity analysis).

Pirfenidone—F. Hoffmann-La Roche Ltd

136/Protocol ML39355, Version 2 dated 09-Jun-2018

- Replacement with an intermediate value (FVC =1500 mL or 50%) (Sensitivity analysis).

Missing data due to reasons other than death (pattern 3) will be replaced with imputed values based on the average measurements for “similar” patients at that time point (Primary analysis). Similar patients are those without missing data before that time point and whose data have the smallest sum of squared deviations (SSD) from that patient for all visits prior to the one with the missing data. Missing data due to lung transplant will be imputed using the SSD method even if the patient dies after lung transplant. A sensitivity analysis will use the data imputed with last observation carried forward method (LOCF).

Complete case analysis will also be performed as a sensitivity analysis.

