4.2. Randomization and Blinding²

Randomization is not planned in the study.

Blinding is not applicable in this open-label study.

5. Sample Size³

Taking into account study design (single group prospective study), sample size was estimated based on feasibility of patient enrollment with precision-based approach. In the ASCEND study primary efficacy endpoint (Percent Predicted FVC) in pirfenidone group changed from 67.8 (11.24) (denoted as mean (SD)) at baseline to 65.3 (14.52) at week 26, with stable disease (decline in FVC < 10 % to 0 %) in 60.1 % of study patients.

The required sample size for two-sided 95% confidence level can be calculated using the following formula:

$$n = \hat{p}\hat{q} \left(\frac{Z_{\alpha/2}}{E} \right)^2 ;$$
$$n = 0.601 \times 0.399 \left(\frac{1.96}{0.125} \right)^2 \approx 58.96.$$

Assuming previous calculations, 60 patients included in the study will be sufficient for study parameters estimation. Taking into account study goals and the notion that the study drug is a product for the treatment of an orphan drug, margin of error of 0.125 is considered sufficient for parameter estimation. For precision-based sample size justification, with a sample size of 60 patients, an expected mean value of 2.5% and standard deviation of 20, distance from the mean to limit of the two-sided 95% confidence interval for the mean Change from Baseline to Week 26 (Percent Predicted FVC) will extend about 5 (margin of error). The SD for change from baseline at week 26 is conservatively estimated based on the results of the ASCEND study as standard deviation for Percent Predicted FVC in pirfenidone group at week 26 (14.52) multiplied by $\sqrt{2}$ (Machin et al., 1997). This is also in line with the results of CAPACITY programme (Noble et al. 2011) in which the SD of changes from baseline was 17 - 20 at week 72.

Taking into account an expected rate of screening failures about 45%, up to 109 patients will be screened for eligibility.

6. General Considerations

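### No planned analysis lets living patients without a Week 26 FVC do worse after leaving, so the sensitivity analyses cannot show how far faster decline would move the primary mean change

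*SAP*

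**What the plan says.** SAP 6.3 sorts patients by availability of the Week 26 FVC. Pattern 3 is those alive at Week 26 without a value, including early withdrawals, missed visits and lung transplants. The primary analysis gives them the mean Week 26 value of the three completers closest on earlier FVC values (SSD). As an alternative, SAP 6.3 states: "A sensitivity analysis will use the data imputed with last observation carried forward method (LOCF").

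The alternatives in SAP 6.3, SAP 8.1 and the footnotes to Table 2.2 are:

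- Analyses 1, 2 and 7: SSD again. Analyses 1 and 2 vary only the value given to deaths; analysis 7 removes out-of-window values.
- Analyses 3 to 5: "Missing data due to reasons other than death (pattern 3) will be replaced with LOCF". Analysis 6 uses LOCF for deaths as well.
- Analyses 8 and 9: pattern 3 and deaths are left out. Protocol 6.2 has the same element: "Complete case analysis will also be performed as a sensitivity analysis".

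For deaths (pattern 4) the SAP argues that the unobserved values would be lower than those of survivors, and it tries three replacement values. Pattern 3 has no counterpart.

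**The concern.** Protocol 1.1 describes IPF as involving "progressive loss of lung volumes, i.e. decreased forced vital capacity (FVC), and decline in exercise tolerance". A patient who withdraws or is transplanted may well be declining faster than one who stays. SSD assumes that such a patient would have followed completers with similar earlier values. FVC is scheduled only at Screening, Day 1, Week 12 and Week 26, so SSD can match on baseline and Week 12 and sees nothing later. LOCF assumes no further change after the last visit. Complete case assumes that those who left resemble those who stayed.

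The trial's primary product is one mean change with its 95% CI. If all rows of Table 2.2 agreed, a reader could take that as robustness to drop-out. For pattern 3, however, the question of a worse course after leaving would not have been asked.

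**Working it through.** **Inputs from the documents.** N = 60. Mean % predicted FVC is 67.8 (SD 11.24) at baseline and 65.3 at Week 26, a change of -2.5 (SAP section 5). The planning values are "an expected mean value of 2.5% and standard deviation of 20".

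**The plan's own figures reproduce.** 0.601 × 0.399 × (1.96/0.125)² = 58.96, rounded up to 60. The half-width for the mean change is 1.96 × 20/√60 = 5.06, stated as about 5.

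**Assumptions, because the documents give no figure.** A fraction d = 10-20% of the FAS lacks a Week 26 FVC. Decline is linear. Those who leave do so after Week 12 and decline k times as fast as stayers (k = 1, 2 or 3). Departure after Week 12 is the normal case for the FAS, which needs a post-baseline efficacy value, and the first one is scheduled at Week 12.

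**Expected values**

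- True mean = -2.5 × [(1-d) + d × k]
- LOCF = -2.5 × (1-d) - d × k × 2.5 × 12/26
- Complete case = -2.5

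| d | k | True | LOCF | Complete case |
|---|---|---|---|---|
| 10% | 1 | -2.50 | -2.37 | -2.50 |
| 20% | 1 | -2.50 | -2.23 | -2.50 |
| 10% | 2 | -2.75 | -2.48 | -2.50 |
| 15% | 2 | -2.88 | -2.47 | -2.50 |
| 20% | 2 | -3.00 | -2.46 | -2.50 |
| 10% | 3 | -3.00 | -2.60 | -2.50 |
| 20% | 3 | -3.50 | -2.69 | -2.50 |

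**SSD can be bracketed.** If matching on Week 12 captured all the extra early decline, the remaining bias would be d × (k-1) × 2.5 × 14/26. If it captured none, the bias would be d × (k-1) × 2.5. For d = 10%, k = 2 this gives 0.13 to 0.25 points; for d = 20%, k = 3 it gives 0.54 to 1.00. Simulation with the three-donor rule (SD of change 4/6 or 6/10 at Weeks 12/26) falls inside these brackets:

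- k = 1: no bias.
- k = 2: 6-13% of the 2.5-point change, about 0.2 to 0.3 points.
- k = 3: 13-27%, about 0.3 to 0.7 points.
- At d = 15%, k = 2: true -2.88, SSD -2.64, LOCF -2.47, complete case -2.49.

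**A sharper post-departure fall.** If 20% fall 10 further points after leaving, the true mean is -2.5 - 0.20 × 10 = -4.5. In simulation SSD and complete case stay near -2.5 and LOCF near -2.2.

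**Does LOCF always lie on the favourable side of SSD?** No. When patients with a steep early or underlying decline were the ones who left (20% missing, Week 12 value available, three sets of assumed SDs), LOCF was below SSD in 47-64% of simulated trials, with mean differences of 0 to 0.11 points. In one such setting all three methods were too favourable (true -2.48, SSD -1.26, LOCF -1.37, complete case -0.53). In another, LOCF roughly matched the truth (true -2.47, SSD -2.32, LOCF -2.50).

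**The case against.** A reader might infer that every alternative for pattern 3 must come out neutral or better than the primary estimate, so that all rows lie on one side of it. The documents do not support that. LOCF keeps a patient's own low Week 12 value while SSD borrows from completers, and the simulations show LOCF below SSD about half the time or more when steep early decliners leave. Complete case also removes deaths, so its distance from the primary result is not due to living drop-outs alone.

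The design also limits the problem. Patients who stop the drug are to continue procedures through Week 26. Those who do form pattern 2, whose observed change is reported separately (Table 2.4), which is direct if partial evidence on discontinuers. One of the two Week 26 days is enough for a value, and pattern 3 includes ordinary missed visits. An assumed 10-20% missing may therefore be generous.

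The shifts are small beside a half-width of about 5. One death imputed as 0% moves the mean by roughly 65.3/60 = 1.1 points. The trial is single-arm and descriptive, with no test or threshold on FVC, so no formal conclusion would reverse.

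All of this stands and limits the weight of the point. It does not fill the gap: the worse-than-observed reasoning is applied to deaths and never to living patients who left, and the CI does not reflect this bias. Because the protocol names LOCF, it should stay in the plan.

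**Conclusion.** The point holds in a limited form. No planned analysis assumes a worse course after leaving for pattern 3, so the nine sensitivity analyses cannot show how far such a course would move the primary mean change. That LOCF and complete case are neutral or more favourable than SSD is an expectation under steady average decline, not a certainty.

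Under the assumed 10-20% missing and two to three times the decline, the SSD estimate is too favourable by about 0.2-0.7 percentage points. This rests on assumed drop-out, linear decline, departure after Week 12 and assumed SDs. A reader might go further and conclude that the trial's primary result is unreliable; the documents do not support that, since they give no drop-out rate and set no decision rule on FVC.

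**What to change.** Keep LOCF and complete case, which the protocol names, and label LOCF as an analysis that stops decline at the last visit. Add to SAP 8.1 and Table 2.2 delta-adjusted SSD rows for pattern 3:

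- For % predicted, take the SSD-imputed Week 26 FVC minus 2.5, 5.0 and 7.5 points (one, two and three times the assumed change).
- For mL, subtract the same deltas converted with each patient's own baseline ratio of mL to % predicted.
- Handle deaths as in the primary analysis, and report the mean change and 95% CI at each delta.

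Each row moves the mean by d × delta: with 10% missing by 0.25, 0.50 and 0.75 points; with 20% missing by 0.50, 1.00 and 1.50. The deltas are a judgement and should be fixed before database soft lock, up to which SAP section 2 allows revisions.

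The cost is some SAP wording and a few programming lines, with no new data. The downside is that the reported range will extend to less favourable values.
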